10.1 Disposition of Participants and Discontinuations

A table of disposition should display the following (per regimen, dose level and in total):

- Number of subjects screened
- Number of subjects who received at least one dose of study intervention (safety analysis set)
- Number of subjects who fulfill the dosing criterion ($\geq 80\%$ of a cohort's dose and at max 5 missed daily dosings) of the DLT analysis set. This number may be higher than the number of subjects screened for a dose level, if subjects receive different dosing than planned.
- Number of subjects with a DLT per investigator's judgement as recorded in eCRF
- Number of subjects with documented end of treatment (of subjects in safety analysis set)

A listing of End of treatment reason will be provided.

CCI

CONFIDENTIAL
INFORMATION

15/38

M3258

First in Human Dose Escalation of M3258 as a Single Agent and Expansion
Study of M3258 in Combination with Dexamethasone

MS201814-0010

Version 2.0

10.2 Protocol Deviations / Exclusion from Analysis Populations**10.2.1 Important Protocol Deviations**

Except for the dosing criterion for the DLT analysis set, this is not applicable for this iAP for SMCs.

10.2.2 Reasons Leading to the Exclusion from an Analysis Population

Subjects who did not receive at least 80% of the planned dose are excluded from the DLT analysis set unless they can be considered in another dose level as described above.

11 Demographics and Other Baseline Characteristics

Not applicable for this iAP, some individual data to appear as part of the patient profiles.

12 Previous or Concomitant Medications/Procedures

Not applicable for this iAP, some individual data to appear as part of the patient profiles.

13 Study Treatment: Compliance and Exposure

Not applicable for this iAP, some individual data to appear as part of the patient profiles.

14 Efficacy Analyses

Not applicable for this iAP, some individual data to appear as part of the patient profiles.

CCI

CONFIDENTIAL
INFORMATION

16/38

M3258

First in Human Dose Escalation of M3258 as a Single Agent and Expansion
Study of M3258 in Combination with Dexamethasone

MS201814-0010

Version 2.0

15

Safety Analyses

The subsections in this section include specifications for summarizing safety endpoints that are common across clinical studies such as adverse events, laboratory tests and vital signs.

The primary endpoint during dose escalation is the occurrence of DLTs, AEs and other safety related measurements.

The analysis population for the DLT analysis will be the DLT analysis set, for all other safety analyses it will be the safety analysis set.

15.1

DLT analysis

The primary objective of the SMC meetings is to regularly monitor the overall safety of the subjects enrolled in the trial. An important part of that is reviewing DLTs. Besides individual medical judgement on DLTs, a summary analysis of DLTs is performed using a Bayesian two-parameter logistic modeling approach to model the relation of dose to the occurrence of DLTs. The results from updating this model will assist the SMC in their dosing decisions.

A listing of DLTs as flagged by investigator in eCRF will be provided. It is possible that there is a discrepancy between final SMC decision of SMC and investigator flag in eCRF. Therefore the title of this listing needs to clearly state "DLTs as per investigator flag in eCRF". The listing will be sorted by regimen, dose level and subject ID. This listing will additionally contain age, sex, type of myeloma, AEterm, SOC, PT, grade, SAE (yes/no), relatedness to M3258 (yes/no), relatedness to dexamethasone (yes/no) (if applicable, in part B only), start date (+treatment day), stop date (+treatment day), duration of DLT, action taken with M3258, if treatment was stopped before start of AE: days since stop of treatment, and outcome.

A DLT profile plot of all subjects in the SAF Analysis Set with DLT decisions from previous SMCs will be produced (per regimen). This will show an open square for all subjects who did not have a DLT, a closed square for those who experienced a DLT, and an open circle for those who were excluded from the DLT Analysis Set. This plot will have Cohort Number or subject index on the x-axis and dose level (mg) on the y-axis.

Bayesian two-parameter logistic model

Summary statistics of the posterior probability distribution of the DLT rate (2.5%, 25%, 50%, 75%, and 97.5% quantiles) for each predefined dose level will be updated by estimation according to the logistic model. Using data from all subjects evaluable for DLT or who experienced a DLT at the completion of a new cohort (and data from all previous cohorts: DLT analysis set), the Bayesian logistic model provides a recommended dose level for the next cohort based on minimal

CCI

CONFIDENTIAL
INFORMATION

17/38

M3258

First in Human Dose Escalation of M3258 as a Single Agent and Expansion
Study of M3258 in Combination with Dexamethasone

MS201814-0010

Version 2.0

loss. This recommendation will be shared with the SMC after the SMC has made the decision upon DLTs. In preparation of the SMC, the model will be updated with potential scenarios' data (e.g. 3 subjects evaluable on current dose level, 0 DLTs, the same with 1 DLT, 2 subjects evaluable 0 DLT etc....), to have the results ready at SMC.

Recommendation is based on a loss function (probabilities of being in 1 of the 4 intervals will be multiplied with a loss term as follows:

$0 * P(\text{target dosing (estimated DLT rate in (0.2-0.35)}) + 1 * P(\text{under dosing (estimated DLT rate in [0-0.2])}) + 2 * P(\text{for over dosing (estimated DLT rate in (0.35-0.6])}) + 3 * P(\text{excessive dosing (estimated DLT rate in (0.60-1])})$.

The recommended dose level resulting from the model for the next cohort is the dose with the lowest loss function. This Bayesian escalation approach will be used to assist the SMC to select the next dose from a predicted set of acceptable doses, i.e., 10 mg, 20 mg, 35 mg, 50 mg. It is possible to choose a dose(s) not within the pre-specified dose-escalation plan. In this case the estimated posterior probabilities of the selected dose will also be provided to the SMC.

The model will continue to be updated at each SMC until the SMC has decided to stop dose escalation.

Prior distribution and likelihood are used to calculate the posterior probabilities based on Bayes theorem.

The likelihood is defined based on a binomial distribution, modelling the rate of subjects with at least 1 DLT.

The relationship between dose and toxicity rate is defined by

$$P(DLT|d_j, \alpha, \beta) = \frac{\exp\left(\alpha + \exp(\beta) * \log\left(\frac{d_j}{d_{ref}}\right)\right)}{1 + \exp\left(\alpha + \exp(\beta) * \log\left(\frac{d_j}{d_{ref}}\right)\right)}$$

Where $d_j \in \{10 \text{ mg, 20 mg, 35 mg, 50 mg}\}$ (or different) and (α, β) are bivariate normally distributed. Reference dose d_{ref} is 90 mg. The chosen prior for monotherapy escalation has the following parameters

$E(\alpha) = -0.708$,

$E(\beta) = -0.389$,

$SD(\alpha) = 1.2$, $SD(\beta) = 0.9$, $Cov(\alpha, \beta) = 0$.

The prior distribution has not been changed compared to the protocol defined.

CCI

CONFIDENTIAL
INFORMATION

18/38

M3258

First in Human Dose Escalation of M3258 as a Single Agent and Expansion
Study of M3258 in Combination with Dexamethasone

MS201814-0010

Version 2.0

Handling of changes in regimen

For different regimens, separate models will be used. In general, the same specifications outlined above will be used for each of these models, applicable to the dose given on the treatment days, unless otherwise specified. This means that in a once daily (QD) regimen, 90 mg as reference dose refers to the dosing of 90 mg daily. In a twice weekly regimen (on day 1,4,8,11, etc) the 90 mg reference dose refers to a dosing of 90 mg on day 1, day 4 etc. The approach is not considering weekly cumulative dosing.

Rationale for keeping the same prior: It is assumed that changes in regimen occur due to the fact that the observed dose-toxicity relationship was not as a priori expected. It is further assumed that after the change in regimen the dose- probability of DLT relationship in the new regimen is coming closer to the a priori expected dose-toxicity relationship.

15.2 Patient profiles

The SMC will receive patient profiles containing:

- Subject disposition (still in trial, or withdrawn with reason for withdrawal)
- Demographics and baseline characteristics (e.g., cancer diagnosis, staging)
- Medical history
- History of disease under study
- Previous and concomitant medications
- Prior anti-cancer drug therapies
- Prior anti-cancer radiotherapy
- Prior anti-cancer surgeries
- Concomitant procedures
- Study drug administration, and dose adjustments
- All serious and non-serious AEs (with details like e.g. grade, start and stop date), including but not limited to:
 - DLTs
 - AESIs
 - AEs leading to dose reduction or temporary discontinuation
 - AEs leading to permanent treatment discontinuation
 - AEs leading to death
- Laboratory data (hematology, coagulation, biochemistry, urinalysis)

CCI

CONFIDENTIAL
INFORMATION

19/38

M3258

First in Human Dose Escalation of M3258 as a Single Agent and Expansion
Study of M3258 in Combination with Dexamethasone

MS201814-0010

Version 2.0

- ECG results
- Vital signs

Patient profiles will be provided for the current cohorts under review and updated patient profiles will be provided for subjects from previous cohorts that had changes from last SMC meeting.

15.3 Adverse Events

The severity of adverse events will be graded using the NCI-CTCAE version 5.0, except where CTCAE grades are missing. No imputation of missing grades will be performed. Adverse events will be coded according to the latest MedDRA version at the time of the data cut-off.

- **TEAEs:** Any AEs that are reported (serious and non-serious) will be considered treatment emergent adverse events (TEAEs), with the exception of those that started prior to the first dose of study treatment (unless a worsening of the event is recorded after the first dosing, in which case the event will be counted as a TEAE), or AEs starting more than 30 days after the last dose of study treatment.
- **Related Adverse Events:** AEs with relationship missing, unknown or yes. Relationship is judged separately for M3258, and dexamethasone.
- **SAEs:** Serious adverse events (as recorded on the AE eCRF page, Serious Adverse Event = 'Yes').
- **AEs Leading to Treatment Discontinuation:** AEs leading to permanent discontinuation of study treatment (as recorded on the AE eCRF page, Action taken with study treatment = 'Drug withdrawn'). Treatment discontinuation is recorded separately for M3258, and dexamethasone.
- **AEs Leading to Death:** AEs leading to death (as recorded on the AE eCRF page, Outcome = 'Fatal').

AEs will be summarized by MedDRA PT as event category and MedDRA primary SOC as summary category. In general, each subject will be counted only once within each PT or SOC.

AEs with missing classifications regarding relationship to study treatment, and those with start date on or after the start of study treatment, will be considered as related to the study treatment.

Missing data handling

Incomplete AE-related dates will be handled as follows:

CCI

CONFIDENTIAL
INFORMATION

20/38

M3258

First in Human Dose Escalation of M3258 as a Single Agent and Expansion Study of M3258 in Combination with Dexamethasone

MS201814-0010

Version 2.0

- If the onset date is missing completely or missing partially – but the onset month and year, or year, are equal to that of the study treatment start – then the onset date will be replaced by the minimum of the start of study treatment and the AE resolution date.
- In all other cases, the missing onset day or month will be replaced by 1.
- Incomplete stop dates will be replaced by the last day of the month (if day is missing only), if not resulting in a date later than the date of participant's death. In the latter case, the date of death will be used to impute the incomplete stop date.
- In all other cases the incomplete stop date will not be imputed. If the stop date of an AE is after the date of cut-off, the outcome of the AE is ongoing at cut-off.
- Further information after cut-off (such as fatal outcome) might be taken from the Safety database and reported separately.

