15.3.1 All Adverse Events

Adverse events will be summarized by worst toxicity (according to NCI-CTCAE version 5.0)] per participant, using preferred term as event category and primary system organ class (SOC).

If an adverse event is reported for a given participant more than once during study intervention, the worst toxicity and the worst relationship to study intervention will be tabulated.

In case a participant had events with missing and non-missing grades, the maximum of the non-missing grades will be displayed.

AE tables will be restricted to TEAEs only. The AE tables will include the number and percentage of subjects with at least one TEAE, by MedDRA SOC and PT (both sorted alphabetically), unless otherwise stated.

All AEs will be tabulated by regimen, dose level and overall in a table showing the incidence of TEAEs, by SOC and PT (both sorted alphabetically).

A listing of all TEAEs will be provided. This listing will be sorted by regimen, dose level and subject. This listing will additionally contain age, sex, type of myeloma , SOC, PT, grade, SAE (yes/no), DLT per investigator (yes/no), relatedness to M3258 (yes/no), to dexamethasone (yes/no) (if applicable, in part B only), start date (+treatment day), stop date (+treatment day), duration of TEAE, action taken with M3258, if treatment was stopped before start of AE: days since stop of treatment, and outcome.

Additionally, a listing of all adverse events grade ≥ 3 (incl non TEAEs) and SAEs will be provided: This listing is to be produced twice, once sorted by regimen, dose level and subject ID

CCI

CONFIDENTIAL
INFORMATION

21/38

M3258

First in Human Dose Escalation of M3258 as a Single Agent and Expansion
Study of M3258 in Combination with Dexamethasone

MS201814-0010

Version 2.0

and once sorted by SOC and PT. These will also include age, sex, type of myeloma, grade, SAE (yes/no), DLT per investigator (yes/no), relatedness to M3258 (yes/no), relatedness to dexamethasone (yes/no) (if applicable, in part B only) start date (+treatment day), stop date (+treatment day), duration of AE, if treatment was stopped before start of AE: days since stop of treatment, and outcome.

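### One sentence in the SMC analysis plan, read as written, codes every adverse event starting on or after first dose as related, even when the investigator recorded it as unrelated

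*SAP*

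**What the plan says.** Section 15.3 of the SMC plan (SAP Appendix 18.1) gives two rules for relatedness.

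- The definition of related adverse events, among the bullets that open the section: "AEs with relationship missing, unknown or yes. Relationship is judged separately for M3258, and dexamethasone".
- A free-standing sentence further down. It first names events whose relationship was left unclassified, then adds a second group and states what happens to both: "and those with start date on or after the start of study treatment, will be considered as related to the study treatment".

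The definition of a treatment-emergent event in that section uses other boundaries. An event that began before first dose is left out "unless a worsening of the event is recorded after the first dosing, in which case the event will be counted as a TEAE". Also left out are late events: "or AEs starting more than 30 days after the last dose of study treatment".

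On outputs, section 15.3.1 states "AE tables will be restricted to TEAEs only", and for repeated events "the worst toxicity and the worst relationship to study intervention will be tabulated". Relatedness to M3258 is a column in five SMC listings: DLTs (15.1), all treatment-emergent events and Grade 3 or higher events with SAEs (both 15.3.1), events leading to discontinuation, interruption or reduction (15.3.2), and events of special interest (15.7).

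Section 15.2 of the main SAP repeats the definition and does not contain the sentence. Protocol Appendix 5 makes unrelated one of the two causality categories available to the investigator.

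**The concern.** The sentence joins two groups of events. The first is limited to missing assessments. The second is limited only by onset date, so it takes in every event that begins on or after first dose, whatever the investigator wrote. For an event recorded as unrelated, the definition and the sentence give opposite answers, and the plan does not say which one governs.

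The SMC uses these listings when it reviews safety. Protocol section 6.6 allows a later-cycle treatment-emergent event to count as a DLT if it is related to study intervention and the SMC considers it significant enough to make further escalation unacceptable. If the relatedness column is positive for every event with onset after first dose, it no longer helps the SMC separate events the investigator attributed to M3258 from those he or she did not. The same event could also be shown as related in an SMC listing and unrelated in the final report.

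**Working it through.** No figure in the plan is at issue, so the check applies each rule to every kind of event that the plan distinguishes.

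**Inputs**
- Recorded relationship: no, yes, unknown, missing (4 values).
- Onset: before first dose; from first dose to 30 days after last dose; later than that.
- For pre-dose onset only: worsened after first dose, or not.

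**Number of event types:** 4 × 2 (pre-dose) + 4 (on treatment) + 4 (late) = 16. Treatment-emergent types: 4 (pre-dose, worsened) + 4 (on treatment) = 8.

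**Rules**
- A, the definition: related if yes, unknown or missing.
- B, the definition plus the sentence as written: related under A, or onset on or after first dose.
- C, the probable intent: related if yes or unknown, or if missing with onset on or after first dose.

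| Event types | A | B | C |
|---|---|---|---|
| Pre-dose, not worsened (4) | 3 | 3 | 2 |
| Pre-dose, worsened (4) | 3 | 3 | 2 |
| First dose to 30 days after last dose (4) | 3 | 4 | 3 |
| More than 30 days after last dose (4) | 3 | 4 | 3 |
| All (16) | 12 | 14 | 10 |
| Treatment-emergent (8) | 6 | 7 | 5 |

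**Results**
1. A and B differ in 14 − 12 = 2 types. Both are events recorded as unrelated, with onset on or after first dose.
2. Among treatment-emergent types, related rises from 6 of 8 to 7 of 8. The one left unrelated under B is a pre-dose event that worsened and was recorded as unrelated.
3. Under B, related and treatment-emergent still disagree in 8 of 16 types: the one just named, plus 7 related types that are not treatment-emergent (3 pre-dose and not worsened, 4 late).
4. C does not rescue the text. If the sentence only adds to the definition, it is redundant, because the definition already counts every missing entry. If it limits the definition, the two disagree on pre-dose events with missing relationship (12 − 10 = 2 types). Those events can appear in the Grade 3 or higher listing, which includes events that are not treatment-emergent.

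These are counts of kinds of event, not of events. The number of records affected is the number with onset on or after first dose that the investigator recorded as unrelated, and the documents do not give it.

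**The case against.** The best case for the plan is that the intent is evident. The labelled definition stands in the same section and again in the main SAP, a careful programmer would follow it, and section 15.3.1 does not say that the column is derived from the later sentence. The SMC also has other safeguards. It receives patient profiles with all adverse events (15.2), it must confirm every DLT (Protocol 6.6), and it sees the model's recommendation only after it has decided on DLTs (15.1). SMC tables and listings are produced only once more than 6 participants have been treated in the study part (section 4). The study has stopped for lack of enrollment (main SAP section 7), so little future dosing depends on this.

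Much of that stands, and it limits the consequence. It does not remove the contradiction, since the plan itself does not secure the intended reading.

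Three stronger conclusions that a reader might infer are not supported:
- *Related and treatment-emergent events become identical in SMC outputs.* They do not; see result 3. The distinction is lost only for onset from first dose to 30 days after last dose. That is still most of what the SMC would see, because routine collection ends at the 30-day safety visit (window ±7 days).
- *The Part A primary endpoint is misreported.* Occurrence of treatment-related events is part of that endpoint, but its analysis for the study report follows the main SAP, which lacks the sentence. The SMC plan specifies no table of related treatment-emergent events.
- *Later-cycle events become DLTs.* Relatedness is necessary under Protocol 6.6 but not sufficient; the SMC's own opinion is still required. Nothing in the documents feeds the derived flag into the Bayesian model.

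**Conclusion.** The sentence is wrong as written. It overrides a valid investigator assessment and contradicts both the definition in its own section and the main SAP. The conflict is confined to events recorded as unrelated with onset on or after first dose: for onset up to 30 days after last dose, 4 of 4 relationship entries count as related instead of 3 of 4. The effect reaches the relatedness column of the five SMC listings and the worst-relationship tabulation, and through them the information before the SMC when it judges later-cycle events. The study report is unaffected.

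This rests on reading the sentence literally. Whether any SMC output was affected depends on which rule was programmed, which the documents do not show.

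**What to change.** Delete the sentence from section 15.3 of the SMC plan and keep the definition as the only relatedness rule, as the main SAP does. A recorded assessment of unrelated is then retained, and missing or unknown entries still count as related. Restricting the sentence to missing relationship with on-treatment onset would be a weaker repair, because it would still disagree with the definition on pre-dose events with missing relationship.

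Then check which rule the SMC listing programs used. If it was the sentence, identify the events recorded as unrelated that were shown to the SMC as related, and note the difference from the final listings.

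The cost is one deleted sentence and a program check, with no new data and no effect on participants.

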15.3.1 All Adverse Events

Adverse events will be summarized by worst toxicity (according to NCI-CTCAE version 5.0)] per participant, using preferred term as event category and primary system organ class (SOC).

If an adverse event is reported for a given participant more than once during study intervention, the worst toxicity and the worst relationship to study intervention will be tabulated.

In case a participant had events with missing and non-missing grades, the maximum of the non-missing grades will be displayed.

AE tables will be restricted to TEAEs only. The AE tables will include the number and percentage of subjects with at least one TEAE, by MedDRA SOC and PT (both sorted alphabetically), unless otherwise stated.

All AEs will be tabulated by regimen, dose level and overall in a table showing the incidence of TEAEs, by SOC and PT (both sorted alphabetically).

A listing of all TEAEs will be provided. This listing will be sorted by regimen, dose level and subject. This listing will additionally contain age, sex, type of myeloma , SOC, PT, grade, SAE (yes/no), DLT per investigator (yes/no), relatedness to M3258 (yes/no), to dexamethasone (yes/no) (if applicable, in part B only), start date (+treatment day), stop date (+treatment day), duration of TEAE, action taken with M3258, if treatment was stopped before start of AE: days since stop of treatment, and outcome.

Additionally, a listing of all adverse events grade ≥ 3 (incl non TEAEs) and SAEs will be provided: This listing is to be produced twice, once sorted by regimen, dose level and subject ID

CCI

CONFIDENTIAL
INFORMATION

21/38

M3258

First in Human Dose Escalation of M3258 as a Single Agent and Expansion
Study of M3258 in Combination with Dexamethasone

MS201814-0010

Version 2.0

and once sorted by SOC and PT. These will also include age, sex, type of myeloma, grade, SAE (yes/no), DLT per investigator (yes/no), relatedness to M3258 (yes/no), relatedness to dexamethasone (yes/no) (if applicable, in part B only) start date (+treatment day), stop date (+treatment day), duration of AE, if treatment was stopped before start of AE: days since stop of treatment, and outcome.

